## **List of abbreviations**

AE	Adverse Event
AESI	Adverse Event of Special Interest
ALT	Alanine aminotransferase/glutamic pyruvic transaminase/GPT
AST	Aspartate aminotransferase/glutamic oxaloacetic transaminase/GOT
ATC	Anatomical Therapeutic Classification
AUC	Area under concentration-time curve
BMI	Body mass index
BP	Blood Pressure
CA	Compartmental Analyses
CI	Confidence Interval
CrCl	Creatinine Clearance
CRF	Case Report/Record Form
CSR	Clinical Study Report
CV	Coefficient of Variation
DAR	Dosage Administration Record
DBP	Diastolic Blood Pressure
DRL	Drug Reference Listing
DT	Dispersible Tablet
ECG	Electrocardiogram
eCRF	Electronic Case Report Form
PRO/ObsRO	Patient Reported Outcomes/Observer Reported Outcomes
EOT	End of Treatment
FAS	Full Analysis Set
FCT	Film Coated Tablet
FU	Follow Up
GCP	Good Clinical Practice
GGT	Gamma-glutamyltransferase
HLT	High Level Terms
IA	Interim Analysis
ICT	Iron Chelation Therapy
IRT	Interactive Response Technology
ITT	Intention To Treat
Kg	Kilogram
LLOQ	Lower Limit of Quantitation
MDRD	Modification of Diet in Renal Disease
MDS	Myelodysplastic syndrome
MedDRA	Medical Dictionary for Regulatory Activities

---

NA	Not Applicable
NCA	Non-Compartmental Analyses
NEU	Neutrophils
NMQ	Novartis MedDRA Queries
PAS	Pharmacokinetic Analysis Set
PDS	Programming Datasets Specifications
PK	Pharmacokinetic
PPS	Per-Protocol Set
PT	Preferred Terms
RBC	Red Blood Cell
SAE	Serious Adverse Event
SAP	Statistical Analysis Plan
SD	Standard Deviation
SCIT	Satisfaction with Iron Chelation Therapy
SI	International System
SMQ	Standardized MedDRA Queries
SOC	System Organ Classes
SCr	Serum Creatinine
TBL	Total Bilirubin
TEAE	Treatment Emergent Adverse Event
TFL	Tables Figures Listings
ULN	Upper Limit of Normal
UNK	Unknown
WBC	White Blood Cell
WHO	World Health Organization

## **1 Introduction**

This document details the planned statistical analysis for data collected in the study CICL670F2202.

Clinical Study Report (CSR) deliverables (tables, figures, listings - TFLs) and further programming specifications are described in separate documents namely TFL Shells and Programming Datasets Specifications (PDS), respectively. This analysis plan describes the primary analysis for the primary CSR planned at the end of the core phase and the analyses for the final CSR planned at the end of the extension phase. One interim analysis is planned to allow for early analysis of the core phase if requested by Health Authority. This document also details the statistical methods to be used for reporting results in the interim CSR.

### **1.1 Study design**

This is a randomized, open-label, multicenter, two arm, phase II study to evaluate treatment compliance and change in serum ferritin of a deferasirox granule formulation and a Dispersible Tablet (DT) formulation in children and adolescents aged  $\geq 2$  and  $< 18$  years at enrollment with any transfusion-dependent anemia requiring chelation therapy due to iron overload, and having a treatment goal to reduce iron burden as measured by serum ferritin.

Patients whose eligibility is confirmed will be enrolled prior to commencing a 48-week randomized treatment period in the core phase with either deferasirox DT (taken as per local label) or deferasirox granule formulation (taken with or without a light meal) beginning on Day 1.

Randomization will be stratified by age groups (2 to  $<10$  years, 10 to  $<18$  years) and by prior Iron Chelation Therapy (ICT) (Yes/No). Up to 240 naïve and pre-treated patients (120 ICT naïve and up to 120 pre-treated) will be randomized.

There will be two study phases which include a 1 year core phase where patients will be randomized to a 48 week treatment period to either Deferasirox DT or granules, and an optional extension phase where all patients will receive the granules up to 5 years. Patients who demonstrate benefit to granules or DT in the core phase, and/or wish to continue in the optional extension phase on granules, will be offered this possibility until there is local access to the new formulation (granules or FCT) or up to 5 years, whichever occurs first.

During the 48 week treatment period in the core phase, patients will return to the site for study assessments weekly for the first 3 weeks and then every 4 weeks starting from week 5 (weeks 9, 13, 17, 21, 25, 29, 33, 37, 41 and 45) until the core End Of Treatment (EOT) visit.

Patients who discontinue study treatment before completing the core or optional extension phase should be scheduled for an end of treatment visit within 7 days of the last dose of study treatment, at which time all of the assessments listed for the core end of treatment visit or extension end of treatment visit will be performed.

All patients, regardless if they discontinue the study treatment early or per protocol, will be contacted for safety evaluations 30 days after the last dose of study treatment.

## 1.2 Objectives

The study objectives as outlined in the [protocol Section 3] are as follows (Table 1-1).

**Table 1-1 Objectives and related endpoints**

Objective	Endpoint	Analysis
Primary		

 
To evaluate both formulations on patient compliance, using stick pack/tablet count over 24 weeks of treatment in ICT naïve patients during core phase
 
To evaluate the change from baseline in serum ferritin after 24 weeks of treatment for both formulations in ICT naïve patients
 
	
 
Compliance measured by stick pack/tablet count over 24 weeks of treatment (i.e. assessed at week 25 visit)
 
Change from baseline in serum ferritin after 24 weeks of treatment (i.e. serum ferritin at week 25 visit)
 
	Refer to Protocol Section 10.4 / SAP Section 2.8
Secondary (Core phase)		
To evaluate both formulations on change in serum ferritin and compliance in ICT naïve patients, after 48 weeks of treatment	
 
Compliance measured by stick pack/tablet count after 48 weeks of treatment
 
Change from baseline in serum ferritin after 48 weeks of treatment
 
	Refer to Protocol Section 10.5 / SAP Section 2.8.5
To evaluate both formulations on change in serum ferritin after 24 weeks and 48 weeks of treatment in ICT naïve and pre-treated patients	Change from baseline in serum ferritin after 24 weeks (i.e. assessed at week 25 visit) and 48 weeks of treatment	Refer to Protocol Section 10.5.1 / SAP Section 2.8.5
To evaluate both formulations on patient satisfaction and palatability using Patient / Observer Reported Outcomes (PRO/ObsRO) questionnaires	Domain scores of treatment satisfaction and palatability over time	Refer to Protocol Section 10.5.2 / SAP Section 2.9.1
To evaluate both formulations on overall safety	Overall safety, as measured by frequency and severity of adverse events (including active monitoring for renal toxicity; including renal failure, hepatic toxicity; including hepatic failure, and gastrointestinal hemorrhage), and changes in laboratory values from baseline (serum creatinine, creatinine clearance, ALT, AST, RBC and WBC). In addition, vital signs, physical, ophthalmological, audiometric, cardiac, and growth and development evaluations will be assessed.	Refer to Protocol Section 10.5.3 / SAP Section 2.9.2
To evaluate compliance using a daily PRO/ObsRO questionnaire	Rate of dosing instructions deviations (doses missed / not taken at the same time every day)	Refer to Protocol Section 10.5.4 / SAP Section 2.9.1
To evaluate pre-dose PK data to support the assessment of compliance	Pre-dose deferasirox concentrations in all patients [except Egypt] at weeks 1, 3, 5, 9, 13, 17, 21, 25, 29, 33, 37, 41 and 45 (13 samples)	Refer to Protocol Section 10.5.5.1 / SAP Section 2.9.3
Post-dose data to be analyzed along with pre-dose PK data	Post-dose deferasirox concentrations between 2 and 4 hours post-dose at Weeks 5 and 9 (2 samples)	Refer to Protocol Section 10.5.5.2 / SAP Section 2.9.3
To explore exposure-response relationships for measures of safety and effectiveness	Serum creatinine change from baseline, notable serum creatinine events, serum creatinine clearance change from baseline and notable serum creatinine clearance events,	Refer to Protocol Section 10.5.5.3 / SAP Section 2.9.3

Objective	Endpoint	Analysis
	urine protein creatinine ratio change from baseline and serum ferritin change from baseline, in relationship to pre- and post-dose deferasirox concentrations.	
Secondary (Optional Extension phase) To assess additional safety data about new formulation (granules) in pediatric population	Overall safety, as measured by frequency and severity of adverse events (including active monitoring for renal toxicity; including renal failure, hepatic toxicity; including hepatic failure, and gastrointestinal hemorrhage), and changes in laboratory values from baseline (serum creatinine, creatinine clearance, ALT, AST, RBC and WBC). In addition, vital signs, physical, ophthalmological, audiometric, and growth and development evaluations will be assessed.	Protocol sections 10.5.3 and 10.6.1 / SAP Section 2.9.2

## 2 Statistical methods

This section will be imported to section 9.7 of the CSR after the analyses have been conducted and follows the CSR template structure as of the release date of the first final version of this document.

[Section 4 Additional details on](#) of the SAP provides statistical and programming conventions.

### 2.1 Data analysis

Data will be analyzed by Novartis Oncology Biostatistics and Statistical Programming personnel according to the data analysis section 10 of the study protocol as detailed in this analysis plan.

SAS® version 9.4 (or later version if available at time of database lock) will be used for all analyses.

Data from all patients who signed informed consent will be used in the analysis. The analysis cut-off date for the primary analysis of study data will be established 24 weeks after approximatively 96 ICT naïve patients have been randomized. For the interim analysis a cut-off date will be established. All randomized iron chelation naïve patients who have completed a minimum of 12 weeks of treatment exposure or discontinued from treatment core phase at the time of the cut-off date will be included in the interim analysis (see [Section 2.12](#)).

All statistical analyses will be performed using all data collected in the database up to the data cutoff date. All data with an assessment date or event start date (e.g. vital sign assessment date or start date of an adverse event) prior to or on the cut-off date will be included in the analysis. Any data collected beyond the cut-off date will not be included in the analysis and will not be used for any derivations.

All events with a start date before or on the cut-off date and an end date after the cut-off date will be reported as 'ongoing. The same rule will be applied to events starting before or on the cut-off date and not having documented end date. This approach applies, in particular, to

adverse event and concomitant medication reports. For these events, the end date will not be imputed and therefore will not appear in the listings.

Subsequent to the primary analysis, the study will remain open to collect efficacy and safety data from core phase and safety data from the extension phase until the end of the study has been declared (all patients have completed the safety follow-up period of the extension phase).

The primary and interim statistical analyses will be performed using the data from the core phase: the core phase is defined as the time period from start of the trial up to the stop date of the core phase as defined in [Table 2-1](#).

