**Figure 4-1**      **Study schema**

## **4.2 Timing of interim analyses and design adaptations**

One interim analysis has been added to allow for early analysis of the data if requested by the health authority. All the analyses included in the interim analysis will be descriptive. The IA will be performed by the Novartis study team. No decisions regarding the future course of the trial is anticipated at the time of the IA and the trial will continue.

All patients randomized in the study and who have completed a minimum of 12 weeks of treatment exposure or discontinued from treatment core phase at the time of the cut-off date will be included in the interim analysis (Section 10.7).

The cut-off for the primary analysis will be 24 weeks after approximately 96 ICT naive patients have been randomized.

The core data analysis is planned when all patients have completed their 48 week study treatment in the core phase including safety follow-up (if applicable).

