## **7 Visit schedule and assessments**

### **7.1 Study flow and visit schedule**

[Table 7-1](#) lists all of the assessments for the core phase and [Table 7-2](#) lists all of the assessments for the optional extension phase and both indicate with an "X", the visits when they are performed. Patients in the core phase who complete Visit 16 and decide to proceed to the optional extension phase will begin following all the assessments included in the visit 777 in [Table 7-1](#) and then follow the optional extension assessment visit 17 listed in [Table 7-2](#) on the

same day so as to avoid a gap in treatment. Patients who were on the DT arm during core phase of study who have switched to granules at Visit 17 as part of the optional extension phase will need to return weekly (Visits 18, 19 and 20) for the first month after beginning the optional extension phase (granules) for serum creatinine and creatinine clearance. Thereafter they will follow the same schedule as patients who were on granules arm during the core phase. Visit 778 should not be completed by patients who continue into the optional extension phase. Should a patient discontinue the core phase at or prior to Visit 16, they should perform Visits 777 and 778 including safety follow up as per [Table 7-1](#).

Patients in the optional extension phase will complete Visit 779 and 780 at the end of the study or in case of earlier discontinuation.

Patients should be seen for all visits to perform the scheduled assessments on the designated day, or as close to is as possible, i.e., for the core phase not exceeding  $\pm$  2 days for assessments scheduled in Visits 1 to 6 and  $\pm$  7 days for all other visits until End of Treatment Visit 777. For the optional extension phase, not exceeding  $\pm$  7 days for all visits until End of Treatment Visit 779. In this clinical trial, a week is 7 calendar days. For yearly assessments in extension phase, i.e. audiology, ocular and growth and development examinations,  $\pm$  30day window is allowed.

All visits should be scheduled respective to the randomization date (Visit 3) for the core phase, rather than in relation to the previous visits. For the optional extension phase, all visits should be scheduled respective to Visit 17.

All data obtained from these assessments must be supported in the patient's source documentation. No eCRF pages will be used as a source document.

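### The primary cut-off leaves no allowance for the week-25 visit window, so late but permitted visits of the last naive patients fall outside the formal analysis

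*SAP*

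**What the plan says.** **Cut-off.** Protocol 4.2 states: "The cut-off for the primary analysis will be 24 weeks after approximately 96 ICT naive patients have been randomized". The primary-analysis SAP, section 2.1, says the same of the cut-off date, which "will be established 24 weeks after approximatively 96 ICT naïve patients have been randomized". Neither text adds days for the visit window.

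**Data kept and dropped.** Under SAP 2.1, data dated "prior to or on the cut-off date will be included in the analysis". The next sentence closes the other side: "Any data collected beyond the cut-off date will not be included in the analysis"; it also bars such data from derivations. SAP Table 2-1 also lists the cut-off date among the dates that can end the core phase.

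**Visit timing.** Protocol 7.1 says: "All visits should be scheduled respective to the randomization date (Visit 3) for the core phase". The tolerance at week 25 is plus or minus "7 days for all other visits until End of Treatment Visit 777". SAP Table 4-2 uses a wider window for assigning laboratory values to weeks, from 14 days before to 13 days after the planned day.

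**Missing values.** SAP 2.8.3 fills a missing week-25 ferritin with the most recent post-baseline value. Compliance is not imputed, and patients who stop before week 25 still contribute a compliance value.

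**The concern.** A cut-off placed on the planned visit day leaves the last patients no room for the lateness that the protocol itself allows. A child still on treatment who attends three days late, within tolerance, would have that visit's ferritin and drug count excluded. The ferritin endpoint would then come from an earlier visit, as it would for a dropout, and the patient would count towards the 10% missing-data trigger for multiple imputation in SAP 2.8.4. The drug count would lack the last return, so compliance would cover roughly 20 weeks rather than 24; the SAP gives no specific rule for a dispensing interval left open by the cut-off.

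What is at stake is the quality of the one formal test. These gaps come from the calendar rule and not from patient behaviour, and they could be avoided.

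**Working it through.** **Inputs.**
- Visits counted from randomisation, tolerance 7 days either way: Protocol 7.1.
- Planned day and analysis window for week 25 (k = 5): SAP Table 4-2.
- Efficacy study day 1 is the day of randomisation: SAP 2.6.
- Cut-off used, 31-May-2018: rationale of Protocol Amendment 6.
- Naive patients randomised, 60 by 15-Jun-2017 and 94 by 06-Dec-2017: rationales of Amendments 4 and 5.
- Difference 450 ng/mL, SD 900 ng/mL, 45 per arm, one-sided 5%, power 76%: SAP 2.11.

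**Step 1: the plan's own figures.** Planned week-25 day = (5 + 4×5 − 1)×7 + 1 = 169, which matches the day printed for week 25 in SAP Table 4-4 (ocular data). The Table 4-2 window is 169 − 14 = 155 to 169 + 13 = 182. The week-21 visit is (5 + 4×4 − 1)×7 + 1 = day 141. For power, the noncentrality is (450/900)×√(45/2) = 2.37 with 88 degrees of freedom; the one-sided 5% t-test has power 76.1%, which reproduces the stated 76%.

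**Step 2: where the cut-off falls.** For the patient who triggers it, the cut-off is randomisation + 24×7 = 168 days, which is study day 169.
- Kept: any visit on or before day 169.
- Dropped although the protocol permits it: days 170–176, or 7 of the 15 days from 162 to 176.
- Dropped although Table 4-2 accepts it: days 170–182, or 13 of the 28 days from 155 to 182.

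A patient randomised d days before the trigger has d more days and loses only a visit more than d days late.

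**Step 3: how many patients were exposed.** 31-May-2018 minus 168 days is 14-Dec-2017. A patient randomised on 06-Dec-2017 reached day 176 at + 175 days, on 30-May-2018, before the cut-off. So the 94 patients randomised by then had their whole protocol window, leaving 96 − 94 = 2.

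Cross-check from accrual: (94 − 60)/174 days = 0.195 per day, giving 1.4 patients in the last 7 days and 2.5 in the last 13. Exposure is not loss. If visit days are uniform over the 15-day window, the average chance of loss for d = 0 to 6 is (7+6+5+4+3+2+1)/(7×15) = 28/105 = 27%, so about 1.4 × 0.27 = 0.4 visits would be expected to be lost.

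**Step 4: effect on the ferritin test.** Assume ferritin changes linearly and a week-21 value replaces week 25. An affected patient then shows 20/24 of the effect, a loss of 28/168. With m of 96 affected, the mean effect is 450 × [1 − (m/96)×(28/168)].

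| m | Mean effect (ng/mL) | Power, 45 per arm |
|---|---|---|
| 0 | 450.0 | 76.1% |
| 2 | 448.4 | 75.8% |
| 10 | 442.2 | 74.8% |

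**Side point on anchors.** The footnote to Table 4-2 counts study day 1 from first treatment, while SAP 2.6 counts efficacy days from randomisation. If dosing starts after randomisation, Table 4-2 day 169 falls after the cut-off.

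**The case against.** The strongest reply is that almost nothing is lost. Visits on the planned day or earlier are kept. The trigger is approximately 96 patients, which leaves some room in choosing the date. Days 177–182 lie outside the protocol's own tolerance, since Table 4-2 assigns data to weeks and does not schedule visits. The End of Core and final SAPs describe the primary analysis as done once 96 naive patients had finished 24 weeks or stopped early. The End of Core SAP (2.8, 2.8.2, 4.5.1) puts cumulative week-24 data from all naive patients through the same ANCOVA, with interval and p-value, so late visits can re-enter there.

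Most of this stands and fixes the size of the point. It does not remove it. Finishing 24 weeks of treatment is not the same as having passed the visit window, and the End of Core analysis is declared descriptive, so the formal test keeps the truncated data. The word approximately does not help either: FAS-1 contains all randomised naive patients, and any randomised after the trigger would reach the cut-off before day 169.

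A reader might infer more: that the last patients' week-25 visits are lost as a rule, or that both co-primary endpoints go missing and are filled by carry-forward. The documents do not support this. Only late visits are lost for the triggering patient, and carry-forward applies to ferritin alone. Compliance is not imputed; the patient keeps a value over a shorter period.

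**Conclusion.** The point holds as a small one. The cut-off rule has no margin for the visit window, so a late but permitted week-25 visit among the last naive patients is excluded from the formal primary analysis. About 2 of 96 patients were exposed to losing a visit within the protocol's tolerance. The power effect, if both were affected, is about 0.3 percentage points.

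A reader might connect this with the End of Core SAP's statement that the study missed its primary objective. Nothing in the documents supports that link, and an effect of this size makes it implausible.

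The estimate assumes that 24 weeks means 168 days, that the 94 patients had been randomised by the date of Amendment 5, that 96 naive patients were counted, and that ferritin changes linearly with an unchanged SD. Individual randomisation and visit dates are not in the documents, so the actual number of lost visits cannot be derived.

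**What to change.** Define the primary cut-off as the date by which the last counted naive patient has completed the week-25 visit, passed its window, or discontinued. Because the day of randomisation is day 1, the window ends at randomisation + 175 days for the protocol tolerance (day 176) or + 181 days to match Table 4-2 (day 182). Against the cut-off used, that is 07-Jun-2018 or 13-Jun-2018 instead of 31-May-2018. The cost is one sentence in each document and at most 13 days' delay.

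The primary analysis is complete, so for this trial the remedy is reporting. State how many FAS-1 patients had a week-25 ferritin carried forward, or a compliance period shortened, only because of the cut-off, and set the End of Core ANCOVA estimates beside the primary ones. This needs no new data collection.

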**Table 2-1      Definition of core and extension phases**

Core phase			Extension phase		
Treatment	Start date	Stop date	Treatment	Start date	Stop date
Granules	Date of first IC signed	Minimum[Date of latest administration of Granules in core phase + 30 days, cut-off date, Visit 17 date – 1 day]	Granules	Visit 17 date	Date of the last administration of Granules in extension + 30 days
DT	Date of first IC signed	Minimum[Date of latest administration of DT + 30 days, cut-off date, Visit 17 date – 1 day]	Granules	Date of first administration of Granules	Date of the last administration of Granules in extension + 30 days

Only data with an assessment date or event start date (e.g. vital sign assessment date or start date of an adverse event) in the core phase will be summarized in the interim and primary analysis.

Summaries will be based on:

- Core phase comparing data for Granules versus DT formulations (blue rectangle in [Figure 2-1](#)).
- Entire granule period of patients randomized to Granule combining core and extension phases (dark green rectangle in [Figure 2-1](#)) side-by-side with Granules for patients randomized to DT who switched to Granules in extension phase (light green rectangle in [Figure 2-1](#)). Cross-over treatment group corresponds to the patients randomized to DT who switched to Granules in the extension phase.

